## Recruitment methods

Members of the study team will communicate with EMS agency directors and individual EMS clinicians using telephone and email communication and other methods as necessary (e.g., in-person communication).

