### Details:

We will use traditional paper-based research study flyers and standardized emails to connect with and recruit EMS agency directors to participate. We will also use a video-based version of our study flyer that can be hosted on our study website ([www.saftie.pitt.edu](http://www.saftie.pitt.edu)) and circulated on social media.

We will communicate directly with EMS agency leaders and with individual EMS clinicians who may be interested in participating in this research study. Once an agency director or individual clinician reaches out to us, they will be screened.

We will ask agency administrators to set a date for opening enrollment. When that date arrives, the agency administration will distribute a paper-based study flyer (a standardized recruitment email) and help to distribute a video-based individual EMS clinician recruitment flyer (as a complement to the paper version) to their crew members via their internal email lists. We will also host the video flyers on our platforms for ease of viewing. We will ask the EMS agency administrators to post the paper-based study flyer in high traffic areas on the EMS organization and to circulate our video-based flyer.

If our communication is with an individual EMS clinician, they will be directed to the study website and asked to complete the screening form. If eligible, they will be assisted with signing up for the study and instructed to watch the video consent on our study website.

We have two recruitment videos. One that shows various aspects of the study and a second video that highlights various aspects of the mobile app.

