At the individual EMS clinician/worker level, we will exclude individuals who primarily work administrative jobs/roles at the agency. We will exclude individuals who answer NO to any of the screening questions (see screening questions in #5 above).

EMS clinician workers are required to have certification / licensure to provide emergency medical services care. These individuals are 18 years or older. Thus no children or persons <18 years of age will be eligible or enrolled.

*Power analysis:*

Our power calculation was designed to determine the number of agencies and individual EMS clinician workers needed to detect an important impact on fatigue and sleep quality.

Given our experience, we feel it appropriate and necessary to have a moderate to low level of the anticipated number of individual enrollees per cluster (agency). With 60 total clusters (30 EMS agencies in the intervention group and 30 in the APC group) and an average of 10 individuals enrollees per cluster, we will have 83.7% power to detect:

[A] a 15% reduction in the point-prevalence of fatigue in the intervention assigned participants versus the APC assigned participants; and

[B] a clinically meaningful change of >3 points on the Pittsburgh Sleep Quality Index from randomization to 3 months and 6 months.

If we enroll a total of 100 EMS agencies (50 EMS agencies in the intervention group and 50 in the APC group) with an average of 5 individuals per cluster (agency), we will have 85.8% power to detect:

[A] a 15% reduction in the point-prevalence of fatigue in the intervention assigned participants versus the APC assigned participants; and

[B] a clinically meaningful change of >3 points on the Pittsburgh Sleep Quality Index from randomization to 3 months and 6 months.

A cluster is defined as an EMS agency with at least 2 individual participants enrolled. Locations (agencies) with 1 or no enrollments will not be considered as counting towards total cluster goal enrollment.

*Statistical analyses:*

The primary outcome for this agency-randomized trial is EMS worker fatigue related to shift work, measured by the CFQ at 3 and 6 months after randomization. To test the effect of the intervention on worker fatigue, we will use a generalized linear mixed model with logit link (due to the dichotomous nature of outcome: fatigued versus not-fatigued). We will use a random agency effect to account for the clustering of EMS workers within

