agencies and a random worker effect to account for the correlation between repeated measures within worker. The main effects of time, intervention, and intervention\*time interaction will be fit as fixed effects with primary focus on the contrast between the intervention and APC groups at 6 months post start of treatment period. The mixed model using both time points allows us to borrow information from the correlation between the time points for those workers with missing data on either time point. We will control for agency size since it will be a randomization stratification factor. We will use a similar approach to compare sleep quality, measured with the PSQI, between enrolled EMS workers at intervention agencies and enrolled workers at APC agencies. This analysis will use a linear mixed model (*assuming normality of these numeric outcomes*) controlling for baseline sleep quality and agency size. We will also report the intraclass correlation coefficients for fatigue and sleep quality to assess our assumptions for sample size analyses. Secondary analyses will adjust for EMS worker characteristics that are potentially imbalanced at baseline and have been shown to be associated with fatigue and sleep quality. Factors include, but are not limited to, years of experience, employment status, shifts per month, number of patients seen during shift, shift length, health status and number of medical conditions.

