**Research activities:**

We will begin recruitment of EMS agencies by disseminating the Study Flyers (and the video-based study flyer) to various EMS agency contacts (e.g., the National Association of State EMS Officials email lists, the National EMS Management Association email lists, the National Association of EMS Physicians email lists, and with other organizations).

We will screen EMS agencies that respond to the study flyer for eligibility using a telephone-based (or via email) screening procedure.

If the initial communication comes from an individual EMS clinician NOT affiliated with an agency that reaches out to us, we will still allow this individual to participate in our study, yet we will not communicate with the agency director unless he/she wishes to communicate with us. In this situation, we may likely have multiple "clusters" with just one participant in it. The individual who decided to sign up for this study is participating as an individual and consenting to participate as an individual.

Next, we will execute / perform our randomization procedure which will determine if the agency (cluster) will be in the Intervention (Sleep/Fatigue) study group/arm or the Active Placebo Control (Teamwork) study group/arm. Once we know the agency's group assignment, we will ask EMS agency administrators to share study flyers (paper and video) with the employees. These study flyers will instruct the individuals within the EMS agency to visit the study designated website ([www.saftie.pitt.edu](http://www.saftie.pitt.edu)) and follow steps for screening for eligibility. If the individual is eligible, he/she will be instructed to follow steps for enrollment.

All enrollment procedures for individual EMS clinician participants will take place on the

study designated website. First, persons who screened-in will be taken to the video consent webpage. Once there, the video consent will play and the individual will have a decision to make regarding participation. He/she will either click on one of two options: [1] I have watched the informed consent video and agree to participate (I ACCEPT) or [2] I DO NOT ACCEPT and do NOT want to participate in this research study.

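### On the administrator route the study team knows an agency's arm before its workers are invited, no concealment from recruiting staff is described, and the primary CFQ model omits baseline CFQ

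*Combined protocol and SAP*

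**What the plan says.** **Order of events.** Research activities describes the administrator route in this order: the agency is screened, then randomised, and then, with the arm known to the team, the next step is "group assignment, we will ask EMS agency administrators to share study flyers (paper and video) with the employees". Workers afterwards screen themselves, watch the consent video and enrol on the website. They answer their first survey once the app is installed.

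**Who recruits.** Recruitment methods states: "Members of the study team will communicate with EMS agency directors and individual EMS clinicians using telephone and email communication". No section says that these staff are kept unaware of the arm, or that someone separate holds the allocation.

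**Primary model.** Under Statistical analyses, the CFQ outcome is taken at 3 and 6 months. The model has time, arm and their interaction as fixed effects, and random agency and worker effects. The only further covariate named is agency size: "We will control for agency size since it will be a randomization stratification factor". The PSQI model, by contrast, is fitted "controlling for baseline sleep quality and agency size".

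**Other adjustment.** Worker-level covariates come in later: "Secondary analyses will adjust for EMS worker characteristics that are potentially imbalanced at baseline". That list is open-ended but does not name baseline fatigue.

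**Baseline CFQ.** Research activities says that the monthly questions resemble the baseline ones. This implies a baseline CFQ without stating it.

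**The concern.** Randomising agencies balances agencies, up to chance. It does not balance the workers who choose to join once the arm is fixed. If recruitment effort differs by arm, or if later workers are influenced by colleagues already receiving sleep or teamwork texts, the arms can differ in fatigue at entry. The primary outcome is self-reported fatigue and one arm's content is about fatigue, so the link is plausible.

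The effect could go either way. More fatigued workers in the sleep/fatigue arm would hide a benefit or look like harm; fewer would mimic a benefit. The random worker effect offers no protection, because arm is constant within a worker. With baseline CFQ neither an outcome row nor a covariate, whatever part of an entry difference lasts to 6 months passes into the primary contrast.

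**Working it through.** **1. Reproduce the plan's power.** Power analysis gives, for 30 agencies per arm, "an average of 10 individuals enrollees per cluster, we will have 83.7% power to detect" a 15% reduction, and for 50 per arm, "with an average of 5 individuals per cluster (agency), we will have 85.8% power to detect" the same. It states no ICC, control prevalence or alpha. I assume two-sided 5%, a normal approximation and a design effect of 1 + (m − 1) × ICC, and read 15% as 15 percentage points. (A relative 15% reduction from 50–60% gives only 27–60% power, so it does not fit.) Solving the two statements together gives ICC 0.070 and p0q0 + p1q1 = 0.478. Prevalences of 50% and 35% give 0.4775.
- 60 × 10: design effect 1.63; SE = √(0.4775 × 1.63/300) = 5.09 points; power = Φ(15/5.09 − 1.96) = 83.8% (stated 83.7%).
- 100 × 5: design effect 1.28; SE = √(0.4775 × 1.28/250) = 4.95 points; power = 85.9% (stated 85.8%).

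**2. SE with no true effect, 60 × 10.** √(2 × 0.25 × 1.63/300) = 5.21 points.

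**3. Entry difference that persists in full.** The plan gives no figure for an entry difference; 3 and 6 points are assumed.
- 3 points: z = 3/5.21 = 0.576. Rejection is 8.3% in the direction of the difference and 0.6% in the other, total 8.9%.
- 6 points: z = 1.151. Rejection is 20.9% and 0.1%, total 21.0%.
- True 15-point reduction with the more fatigued workers in the sleep/fatigue arm: power falls from 83.8% to Φ(12/5.09 − 1.96) = 65.4% or Φ(9/5.09 − 1.96) = 42.3%.

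Across ICC 0.02–0.10 and both trial sizes, simulated false-positive rates are 7.9–10.3% (3 points) and 18.9–27.1% (6 points).

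**4. Entry difference that mostly regresses.** Simulation used 10,000 replicates per scenario, a latent-normal binary CFQ, a cluster-mean t-test, 60 × 10, ICC 0.07 and a baseline-to-6-month correlation of 0.3. About 1.3 or 2.4 points remain at 6 months. The false-positive rate is 5.4% or 7.6%, and power is about 77% or 69%. The cruder product of difference and correlation leaves 0.9 or 1.8 points, giving 5.3% or 6.4%. At correlation 0.5 the simulated rates are 6.5% and 12.0%.

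**5. What baseline CFQ would do to the bias (same simulation, correlation 0.3).**

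| Entry difference | Bias left at 6 months, unadjusted → adjusted (points) | False-positive rate, unadjusted → adjusted |
|---|---|---|
| 3, regressing | 1.3 → 0.3 | 5.4% → 5.1% |
| 6, regressing | 2.4 → 0.6 | 7.6% → 5.5% |
| 3, persistent | 3 → 2.1 | 8.2% → 7.3% |
| 6, persistent | 6 → 4.2 | 20.3% → 15.3% |

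**6. What it would do to precision.** With slope b = 0.3, the adjusted SE is √((2/30) × [V(1 + b²) − 2bC]). V is the variance of an agency mean: 0.25 × 0.07 + 0.25 × 0.93/10 = 0.0175 + 0.02325 = 0.04075. C is the covariance of an agency's baseline and 6-month means. With worker-level correlation 0.3 (total covariance 0.3 × 0.25 = 0.075) and agency-level correlation r, C = 0.0175r + (0.075 − 0.0175r)/10.
- r = 1.0: C = 0.02325, SE 4.5 points
- r = 0.6: C = 0.01695, SE 4.8 points
- r = 0.3: C = 0.01223, SE 5.0 points

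**7. Check with a model close to the planned one.** This was a logistic mixed model with both follow-ups and a Wald test at 6 months, agency size omitted, 1,000 replicates. Monte Carlo error is about 0.8 points near the no-shift rate and up to 1.3 near 20%.

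| Entry difference | Without baseline CFQ | With baseline CFQ |
|---|---|---|
| None | 6.3% | 7.0% |
| 3, persistent | 9.5% | 8.9% |
| 6, persistent | 21.2% | 16.0% |
| 6, regressing | 9.5% | 7.2% |

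Read against the 6–7% rate with no shift, the covariate shows no clear gain at 3 points and a partial gain at 6.

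**The case against.** The procedures leave little room for a recruiter to influence who joins. Agency administrators send out standardised flyers and email, workers screen and consent on the web against fixed questions, the welcome text uses a study name covering both arms, and the control is active with the same message timing. No section gives staff discretion over which eligible workers enrol. The team also anticipated imbalance, since its secondary analyses adjust for worker characteristics. Finally, the entry differences above are assumptions, and the largest figures need them to last undiminished for six months.

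Most of this stands, and it keeps the point modest. A reader might infer that administrators or workers know the arm when they decide, or that enrolment was in fact selective. The documents support neither: it is only the study team that is said to know. A reader might also take the offer of sign-up help under Recruitment methods, Details, as arm-aware staff steering enrolment. That sentence concerns clinicians who make contact individually, and on that route the first clinician comes forward before the agency is randomised. The coordinator's handling of unverified agency names likewise comes after the worker has accepted, and a new agency may not yet have an arm.

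The mitigations do not amount to concealment, however, and secondary adjustment does not alter the primary result. The PSQI analysis is described as similar to the CFQ analysis, but that does not carry its baseline covariate back to the CFQ model.

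**Conclusion.** The point holds as a design risk with a cheap remedy. On the administrator route, allocation precedes invitation, consent and first survey; the team knows the arm; no concealment from recruiting staff is described; and the primary model lacks the baseline covariate that the PSQI model has.

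Its size cannot be fixed from the documents. For assumed entry differences of 3 or 6 points (60 × 10, ICC 0.07 back-solved from the stated power), the false-positive rate runs from near nominal (5.4% or 7.6%) to about 9% or 21%, depending on persistence. The upper figures are a bound under full persistence, not an expectation. The excess lies almost wholly in the direction of the entry difference, so it may hide benefit as readily as create it. It would also be too strong to say that baseline adjustment cures the problem: it removes most of a regressing difference but only part of a persistent one. The case for change rests on the gap in the text and the low cost of closing it. The change should be made; confidence is medium.

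**What to change.** **Main change (Statistical analyses).** Add baseline CFQ as a fixed effect in the primary CFQ model, as is already done for PSQI. State that the first survey includes the CFQ, and give a rule for workers who have no baseline value. The cost is one covariate and that rule. The covariate may also improve precision, from an SE of 5.2 to about 4.5–5.0 points at worker-level correlation 0.3, depending on how stable the agency effect is.

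**Supporting change (Research activities).** Have the platform, or a person who does not recruit, hold the allocation. Do not release it to staff who recruit or assist sign-up while that agency is still enrolling. This is a single window per agency and may last until new enrolment closes in July/August 2023, so arm-specific queries need to go to someone else throughout. It does not stop later workers from hearing about message content from colleagues, and baseline adjustment offsets that route only in part.

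**Reporting.** Show numbers enrolled and baseline CFQ by arm, so that readers can judge whether enrolment differed. The cost is two table rows.

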## **Consent procedures**

Waiver to document written / signed consent form approved.

All potential participants will view a video-based consent made available on the study designated website. We will use a video-based consent procedure whereby the potential participants watch a video version of the consent form and make a decision to [1] I have watched the informed consent video and agree to participate (I ACCEPT) or [2] I DO NOT ACCEPT and do NOT want to participate in this research study. We are requesting a waiver to document informed consent for all study subjects because it will be obtained via video-based methods. Our study is nationwide, which makes it extremely difficult to obtain written consent from all participants. We will still obtain consent from the subjects to participate via video, which does not increase risk. The study involves text messages, a mobile app, and continuing education videos. None of these normally require written informed consent.

### *Minimize coercion and undue influence:*

Potential participants will be allowed to rewind and watch the consent video multiple times if needed. They can also email or call the study team prior to selecting the ACCEPT or DO NOT ACCEPT options for consent.

### *Ensure understanding:*

Our consent video will provide a detailed description of the study. Potential participants will again be allowed to rewind and watch the consent video multiple times if needed. They can also email or call the study team prior to selecting the ACCEPT or DO NOT ACCEPT options for consent.

## **Data safety monitoring**

We will regularly report on progress with recruitment, enrollment, data collection, and any unexpected issues to the Department of Emergency Medicine's Data Safety Monitoring Committee (DSMC). The DSMC will meet at least once per month.

## Protecting privacy

Only members of our research team are involved in this study protocol. No research findings will be provided to participant family members, insurance companies, employers, or any third party without the participant's authorization.

All data that we collect for this research study will be assigned an ID number only when received by our computerized data collection system. We will maintain a data file that contains the participant's name, mobile telephone number, and email address. This file will be located on a computer server and kept separate from the other data. This file will be password protected and access to will be restricted to core members of the research team.

This research study is also covered by a Certificate of Confidentiality (CoC) from the Centers for Disease Control and Prevention (CDC). The researchers with this Certificate may not disclose or use information, documents, or data that may identify the participant in any federal, state, or local civil, criminal, administrative, legislative, or other action, suit, or proceeding, or be used as evidence, for example, if there is a court subpoena, unless the participant has consented for this use. Information, documents, or data protected by this Certificate cannot be disclosed to anyone else who is not connected with the research except, if there is a federal, state, or local law that requires disclosure (such as to report child abuse or communicable diseases but not for federal, state, or local civil, criminal, administrative, legislative, or other proceedings); if the participant has consented to the disclosure, including for his/her medical treatment; or if it is used for other scientific research, as allowed by federal regulations protecting research subjects.

Upon completion of this research study, we will de-identify all data, expunge all files that contain mailing addresses used for remuneration, and add a new randomly generated ID number to all records. All previously used ID numbers will be removed, therefore creating a new dataset with a new randomly generated ID assignment for each record. We will publish the study findings in aggregate in peer-reviewed medical journals. We will do everything possible to protect the participant's privacy.

### **Termination, withdrawal, or attrition**

If a participant has not responded to study related text queries, or monthly surveys over multiple months, the study team will attempt to contact the participant to determine if he/she is still participating. The PI and co-investigators will meet to discuss these cases and make a group / consensus decision to classify the participant as withdrawn OR to continue attempts to reestablish communication over a specified period of time (e.g., up to a one month). If the team's attempts to contact the participant are unsuccessful, the team will monitor activity for one additional month, and if at that time there is no communication, the participant may be classified as "withdrawn" or "lost to attrition," and his/her account on the study website will be suspended.

If a participant withdraws from the study, we will reach out to the participant with a standard email. That email will [1] acknowledge the participant's withdrawal; [2] thank the participant for his/her time commitment to the study prior to withdrawing; and [3] extend an offer to the participant to contact the study team any time with questions. Our study does not have a category of partial withdrawal.

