## **Compensation / remuneration offered to participants**

Our remuneration package for study participants will include \$25 dollars to sign up/enroll, followed by \$10 distributed for months 1 to 5, and then \$25 at the end of the 6-month study distributed on the 6th month of participation. In total, a study participant who participates for the full 6 months may accumulate a total of \$100 in remuneration.

We will also mail directly to participants several popular EMS novelty items. These include coffee mugs, glove pouches, EMS shoulder patches, challenge coins, wallet sized reference index cards for special patient groups (e.g. burn patients), ball point pens, water bottles, keychains, and flashlights. We will mail these items monthly when a participant completes a monthly survey.

In addition, we will reimburse participants for smartphone data and text message use during participation. We will send active participants \$50 at month 3 and \$50 at month 6. We will issue this reimbursement for expenses on the University of Pittsburgh Vincent MasterCard.

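### Silent workers can be classed as withdrawn before month 6 without asking to leave, and nothing in the plan keeps the 3- and 6-month CFQ open to them

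*Combined protocol and SAP*

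**What the plan says.** The rule is in Termination, withdrawal, or attrition. Its trigger reads "If a participant has not responded to study related text queries, or monthly surveys over multiple months", with no number of months given. The study team then tries to reach the worker. The investigators meet on each case and "make a group / consensus decision to classify the participant as withdrawn OR to continue attempts to reestablish communication". The length of those further attempts is given only as an example, up to one month. If they fail, "the team will monitor activity for one additional month". A worker who is still silent may then be classed as withdrawn or lost to attrition, and "his/her account on the study website will be suspended". The section adds: "Our study does not have a category of partial withdrawal".

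The Statistical analyses part of Study design models the CFQ at 3 and 6 months, with "primary focus on the contrast between the intervention and APC groups at 6 months post start of treatment period". It relies on the mixed model to borrow across the two time points when one of them is missing. Baseline adjustment is described for sleep quality, not for fatigue.

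Under Research activities, surveys are answered monthly in the mobile app, which is opened with a code number. Signing in to the study website is a separate step with a password.

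**The concern.** The point is about workers who stop answering, not those who ask to leave or text STOP. Silence is not withdrawal of consent, yet the rule lets the team turn it into full withdrawal before the primary time point, case by case and without stated criteria. With no partial-withdrawal status, there is no category for a worker who has gone quiet but is still followed for outcome. No other passage says that such a worker still gets the 3- or 6-month CFQ, a reminder or the payment.

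What is at stake is avoidable loss of the primary outcome, settled by a discretionary decision rather than by the participant. The trial studies fatigue in shift workers, so it is plausible that going silent is related to fatigue. The documents neither show nor exclude this.

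**Working it through.** The plan gives no figure for this point: no number of missed months, no attrition rate, and no attrition allowance in the power analysis. The check is therefore month arithmetic on the stated rule.

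**Inputs**
- L: month of last response, counted from the worker's own start (my convention).
- Trigger: number not stated. I take 2 and 3 missed months as the range (assumption).
- Further contact: up to 1 month (the section's example).
- Monitoring: 1 month (stated).
- Primary contrast: month 6 (stated).

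**Formulas.** Full path ends at L + trigger + 1 + 1. Classification at the first team review comes at L + trigger at the earliest, which allows no time for the initial contact attempt or the meeting.

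| Trigger | Path | Falls at | Before month 6 if |
|---|---|---|---|
| 2 months | full | L + 2 + 1 + 1 = L + 4 | L < 2 |
| 3 months | full | L + 3 + 1 + 1 = L + 5 | L < 1 |
| 2 months | first review | L + 2 | L < 4 |
| 3 months | first review | L + 3 | L < 3 |

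On the full path with a 2-month trigger, a last response at baseline leads to suspension at about month 4. A last response at month 1 leads to month 5, at month 2 to month 6, and at month 3 to month 7. If the contact period were cut to almost nothing, the path would end at L + 2 + 0 + 1 = L + 3, so no earlier than about month 3.

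**Which CFQ is at risk.** On the full path it is the 6-month CFQ, because the path ends at month 3 or later. The 3-month CFQ is at risk only at first review with a 2-month trigger: L + 2 < 3 gives L < 1.

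**What the model can recover.** A worker last heard from before month 3 who does not return has neither CFQ. The fatigue model then holds no outcome for that worker and has nothing to borrow from. Everyone caught by the full path (L < 2 or L < 1) is in this group. A worker who answered at month 3 and was classed as withdrawn at about month 5 still contributes the 3-month value.

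**Scale of missing outcomes in general.** The power analysis states 83.7% for 60 agencies of 10 and 85.8% for 100 agencies of 5. Alpha, the intraclass correlation (ICC) and control prevalence are not stated. I assume a two-sided 0.05 test of two proportions, control prevalence 0.50 to 0.65, an absolute 15-point reduction, and effective n per arm = k·m / (1 + (m − 1)·ICC), for k agencies of m workers per arm. Solving for 83.7% gives an ICC of about 0.064 to 0.068. The same ICC gives 85.3% to 85.6% for the second design, close to the stated 85.8%.

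At prevalence 0.55 and ICC 0.0639, effective n is 300 / (1 + 9 × 0.0639) = 190 per arm. If 10% of 6-month outcomes are missing (assumed), it is 270 / (1 + 8 × 0.0639) = 179, and power is about 81%. Assumed losses of 20% and 30% give about 78% and 75%. These are losses from any cause. The rule could account for only part of them.

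**The case against.** The strongest case against is that the section may cost no outcomes at all. A reader might infer that suspension shuts off the 6-month CFQ. The documents do not say so: the suspended account is the website one, while the surveys run in the app. What stands is narrower. The worker has been classed as withdrawn, and nothing says that the survey is still sent or that the app stays open.

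A reader might also infer that a worker silent from baseline can be suspended at month 2. Suspension is stated only after failed contact and a further month of monitoring. Contact is also attempted before the team meets, so an immediate decision may cover workers who reply that they have stopped. The text does not restrict it to them, so early classification remains possible, but early suspension is not stated.

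It is tempting to call month 6 the best-paid contact and so the likeliest to bring a worker back. The $25 is paid "at the end of the 6-month study distributed on the 6th month of participation", but the $50 sent at months 3 and 6 is reimbursement for data and texts, and goes to active participants. With it, month 3 carries $10 + $50 = $60. The documents do not support a claim about which payment works.

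A reader might put a number on recoverable outcomes. No document gives a rate of silence or of return. Applying a rate to everyone who falls silent would also count those whose path ends after month 6.

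Finally, the team knows each agency's arm, and no passage masks the decision. That does not show that closure differs by arm; the rule is worded alike for both.

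The section does require contact attempts, and its final classification is permissive. Both soften the rule, but the permissive wording is the same unguided discretion.

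**Conclusion.** The concern holds in a limited form. The plan lets a worker who never asked to leave be classed as withdrawn or lost to attrition before the primary time point, by unguided decision, and it nowhere keeps the 3- and 6-month CFQ open to that worker. The timing rests on reading the undefined trigger as 2 or 3 months and on the one-month contact example. The number of 6-month outcomes affected is unknown and probably small: the full path reaches only workers silent from very early on, who have already passed over several surveys and direct contact. Neither bias nor a material loss of power is demonstrated. The change is worth making because it is cheap and protects the primary outcome.

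**What to change.** Rewrite the paragraph in Termination, withdrawal, or attrition so that:
- a participant who stops responding is classed as *inactive*, not withdrawn;
- inactive participants keep app and website access, and continue to be sent the 3- and 6-month surveys, with the survey payment if completed, until the 6-month window closes;
- classification as withdrawn and account suspension follow only an explicit request to leave, or the end of that window;
- the number of missed months that makes a participant inactive is stated, and this fixed rule replaces the case-by-case decision, identically in both arms.

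The cost is one protocol paragraph and a platform setting, a few more automated reminders, accounts left open somewhat longer, and some month-6 payments to workers who return.
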